11.2.1 Classification of Adverse Events by Intensity/Severity

All adverse events should be graded on a four-point scale (mild, moderate, marked, severe) for intensity/severity. These definitions are as follows:

- Mild:** Transient discomfort; no medical intervention/therapy required and does not interfere with daily activities.
- Moderate:** Low level of discomfort or concern with mild to moderate limitation in daily activities; some assistance may be needed; minimal or no medical intervention/therapy required.
- Marked:** Considerable discomfort with limitation in daily activities, some assistance usually required; medical intervention/therapy usually required.
- Severe:** Extreme discomfort and limitation in daily activities, significant assistance required; *significant* medical intervention/therapy required.

There is a distinction between the severity and the seriousness of an adverse event. Severity is a measurement of intensity; thus, a severe reaction is not necessarily a serious adverse event (SAE). For example, a headache may be severe in intensity, but would not be serious unless it met one of the criteria for serious adverse events.

11.2.2 Expectedness

All AEs will be evaluated as to whether they are expected or unexpected.

- Expected (anticipated):** An adverse event is expected when the nature, severity, or degree of incidence was previously described.
- Unexpected (unanticipated):** An adverse event is unexpected when the nature, severity, or degree of incidence was not previously described.

11.2.3 Relatedness

The study investigator will evaluate if the AE is related to the MobiusHD system. Relationship is defined in the following manner:

Not related: Evidence indicates no plausible direct relationship to the study device, such that:

- A clinically plausible temporal sequence is inconsistent with the onset of the AE and device administration; and/or
- A causal relationship is considered biologically implausible
- The AE can be attributed to concurrent/underlying illness, other drugs, or procedures.

Related: Evidence indicates a reasonable temporal sequence of the event with the study device administration exists, or that the association of the event with study device administration is unknown and the event is not reasonably supported by other conditions, such that:

- There is a clinically plausible time sequence between onset of the AE and study treatment administration; and/or
- There is a biologically plausible mechanism for study treatment causing or contributing to the AE; and
- The AE cannot be reasonably attributed to concurrent/underlying illness, other drugs, or procedures.

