11.3 ANTICIPATED ADVERSE EVENTS

Adverse events that are anticipated to occur during the study are listed below.

- Death;
- stroke/CVA, TIA or seizure;
- vessel damage, dissection, occlusion, aneurysm, perforation, Post-Procedure neck pain, guidewire perforation, rupture or injury;

- damage to, fracture, fragmentation, or dislocation of the implanted device;
- embolization of air, thrombus, or other embolic debris;
- end organ ischemia, vessel thrombosis, or spasm;
- hypotension/hypertension (acute/subacute to 30 days);
- hypotension/hypertension (chronic>30 days);
- hypertension recurrent;
- infection (local or systemic);
- myocardial infarction;
- puncture site complications (i.e. vessel occlusion, hemorrhage; hematoma, pseudoaneurysm or arteriovenous fistula, excessive blood loss);
- renal insufficiency, kidney failure, hematuria;
- bleeding complications;
- bradycardia or arrhythmias including ventricular fibrillation or tachycardia;
- unintentional detachment or implantation of a component of the system, inappropriate sizing of the device;
- drug reaction;
- allergic reaction to contrast media, medications or device materials; and
- emergent surgery.

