13.0 STATISTICAL METHODS

Since this is a pilot study designed to evaluate the initial safety of the MobiusHD in subjects with stage 2 hypertension, no formal hypothesis testing is planned. Complete data for each study subject will be presented in an individual patient profile consisting of all CRF fields and a narrative summary. Additionally, where appropriate, descriptive statistics will be used to tabulate and summarize study outcomes. Background and demographic characteristics will be presented. Continuous variables will be summarized by descriptive statistics (sample size, mean and standard deviation, median, minimum and maximum). Discrete variables will be summarized by frequencies and percentages. Adverse events will be summarized by presenting the number and percentage of patients having any adverse event. Any other information collected (such as severity or relationship to study device) will be listed as appropriate. Any statistical tests performed to explore the data will be used only to highlight any interesting comparisons that may warrant further consideration.

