16.0 MONITORING OF THE STUDY AND QUALITY CONTROL

16.1 DSMB

All SAEs will be evaluated by the DSMB for potential relationship to the investigational device or procedure. All AEs will be evaluated by Sponsor for significance and relevance with respect to trends that may represent a previously unknown or unanticipated risk that may relate to the investigational device or procedure.

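### Section 11.2.3 does not exclude the implant procedure from the alternative causes, so its complications can be entered as Not related

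*Combined protocol and SAP*

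**What the plan says.** Section 11.2.3 sets the question: "The study investigator will evaluate if the AE is related to the MobiusHD system". There are two possible answers.

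- *Not related* opens with "Not related: Evidence indicates no plausible direct relationship to the study device, such that", followed by three bullets: implausible timing, biological implausibility, and "The AE can be attributed to concurrent/underlying illness, other drugs, or procedures". The first bullet ends in and/or. Nothing joins the second to the third.
- *Related* also has three bullets. The first is "There is a clinically plausible time sequence between onset of the AE and study treatment administration; and/or" and the second is a plausible biological mechanism. The word 'and' then leads to the third: "The AE cannot be reasonably attributed to concurrent/underlying illness, other drugs, or procedures".

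Neither list says which procedures are meant, and no category exists for events caused by the implant procedure.

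Section 16.1 sets a wider standard for serious events: "All SAEs will be evaluated by the DSMB for potential relationship to the investigational device or procedure". It also has the sponsor review all AEs for trends that may point to a new device or procedure risk. Section 11.3 expects procedural complications, for example "puncture site complications". On the use of the relatedness entry, Section 13.0 says: "Any other information collected (such as severity or relationship to study device) will be listed as appropriate".

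**The concern.** In a first-in-man implant study, the safety question is what happens to a patient who has the system placed. That includes femoral access, angiography, guidewire passage and contrast as well as the implant itself. A relatedness rule that treats procedures as an alternative cause, without setting the index procedure apart, lets the investigator attribute a complication of the implantation away from the investigational treatment.

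Peri-procedural events are also what the staged 7-day reviews (Section 1.0, Study Enrollment) are placed to catch, and bilateral treatment adds a second carotid implantation. A listing that shows such events as Not related would give later readers an attribution more favourable than the facts. The investigator and the DSMB could also record different answers for the same SAE because they were asked different questions.

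**Working it through.** The plan gives no figure to reproduce here, so the check sets the text side by side.

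**1. The form of the rule.** Let T be plausible timing, M a plausible mechanism, and A reasonable attribution to illness, drugs or procedures. As written, Related = (T and/or M) and not A. The argument rests on that 'and'. It does not need the third Not related bullet to be sufficient alone, which the text leaves open because that bullet has no connector.

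**2. What the system covers.** Sections 2.1.3 and 3.1 define it as the implant plus the Delivery Catheter. Section 3.1 describes guidewires and guiding catheters or sheaths as separate commercial products. Femoral access (Section 3.1) and the arch and carotid angiography and heparin (Section 8.9) are steps of the procedure and not components of the system.

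**3. The rule applied to an access-site bleed after implantation.** T holds.

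| Reading of 'procedures' | A | Related criteria met? | Entry |
|---|---|---|---|
| Any procedure, including the index one | true | no | Not related |
| Only procedures other than the index one | false | yes, through T | Related, though the question asked is about the system |

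The entry depends on the reading. On the second reading the event passes the bullets for Related, but the form still asks about the MobiusHD system, which did not cause it. Neither reading offers a field that describes the event correctly. The same holds for a perforation by a commercial guidewire or a contrast reaction.

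**4. Which expected events are exposed.** Section 11.3 has 19 entries. The puncture-site entry is wholly procedural by its wording. The vessel-injury entry names guidewire perforation, the embolization entry includes air, and the allergy entry includes contrast media. Those three also cover events that the implant could cause, so they are exposed only in part.

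**5. Where the entry is used.**

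- Primary outcome (Section 1.0): all SAEs and UADEs from implantation through six months. The SAE count has no relatedness filter.
- UADE (Section 11.1.2): has its own causality wording and does not refer to Section 11.2.3.
- AE recording (Section 11.2): every AE is recorded whatever its attribution.
- SAEs (Sections 11.5 and 16.1): the DSMB adjudicates them and considers device or procedure.
- Non-serious AEs: the investigator's entry plus the sponsor's trend review. No DSMB judgment of relationship is specified.
- Analysis (Section 13.0): relationship is listed.

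**6. Scale.** No related-event rate is planned and the documents give no misclassification rate. If a reader derived a rate from the listing, one misclassified subject would move it by 1/20 = 5 percentage points overall, or 1/10 = 10 points within one cohort.

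**The case against.** The strongest reply is that 'other' governs both nouns, so the bullet means other drugs or other procedures, that is, causes outside study treatment. The surrounding text gives this some support: the Related bullets speak of study treatment, and the Delivery Catheter is part of the system, so delivery events fall at least partly inside it. The reply stands as far as it goes. The documents do not support saying that implant complications *are* scored as unrelated, only that they can be. It does not remove the defect. The trial has no study drug, so 'other' cannot mean other than the study's own drug. It more naturally means other than the device, and that still takes in the implant procedure. The opening condition for Not related likewise speaks only of the device.

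The second reply is that the safeguards are substantial. The DSMB assesses every SAE on a device-or-procedure basis, each subject has a full profile and narrative, and the move to bilateral implantation rests on DSMB review of the data and FDA approval, with no stated dependence on the investigator's relatedness entry. This stands for SAEs. It does not reach the relationship entry for non-serious AEs, and Section 11.2.3 is the only written definition of relationship in the protocol body.

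Two stronger inferences should be resisted. A reader might conclude that the primary outcome is undercounted; it is not, because SAEs count regardless of attribution. A reader might also conclude that UADEs inherit the bias. Their definition is separate, and it requires an effect not previously identified, whereas Section 11.3 already lists the typical procedural complications as anticipated.

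**Conclusion.** The point holds as a wording defect with a limited reach. Section 11.2.3 permits a complication of the index procedure to be entered as Not related, offers no category that fits it, and does not match the standard in Section 16.1. What is at risk is the investigator's relatedness listing, mainly for non-serious AEs. The SAE component of the primary outcome and the UADE definition are unaffected.

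The size cannot be estimated, because it depends on how investigators read one word. The shifts of 5 and 10 points apply only to a rate that the plan does not define. A reader might infer that the plan will tabulate an understated related-event rate, but Section 13.0 commits only to listing relationship as appropriate.

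The conclusion assumes that the sample case report forms in Appendix III, whose content is not in the text reviewed, do not already contain a separate and defined procedure-relatedness field.

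**What to change.** 1. In the third bullet of both definitions in Section 11.2.3, replace the unqualified term with *procedures other than the index angiography/implant procedure*.
2. Record two judgments for each AE, as separate fields: relationship to the device system and relationship to the index procedure.
3. Apply the same device-or-procedure definitions to the investigator's assessment and to the DSMB's assessment in Section 16.1.
4. In Section 13.0, state that AEs will be listed by both fields.

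The cost is one extra case report form field and a few lines of protocol text. The related-event listing may look less favourable. The change is best made before enrolment, since events already entered under the present wording would have to be reassessed. A third field for protocol-required drugs, or a new main table of attributed events, would go beyond what this defect needs.

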2.0 BACKGROUND AND INTRODUCTION

Normal or optimal blood pressure (BP) is defined as the level at which minimal vascular damage occurs. The Joint National Committee 7 (JNC 7) defines normal BP as a systolic BP (SBP) less than 120 mmHg and diastolic BP (DBP) less than 80 mmHg.¹

An estimated 76 million adults above the age of 20 have high blood pressure in the United States. Data from NHANES 1999-2006 found that approximately 8% of US adults have undiagnosed hypertension. Approximately 30% of adults are unaware of their hypertension, greater than 40% are not on any treatment and two-thirds of hypertensive patients are not being controlled to BP levels <140/90 mmHg.¹ The highest prevalence of hypertension in the US is noted in African Americans.

Worldwide prevalence estimates indicate that hypertension may affect as many as 1 billion individuals, and approximately 7.1 million deaths per year may be attributable to hypertension.¹ The World Health Organization reports that suboptimal BP (>115 mmHg SBP) is responsible for 62% of cerebrovascular disease and 49% of ischemic heart disease (IHD), with little variation by sex. In addition, suboptimal BP is the number one attributable risk factor for death throughout the world.¹

Blood pressure control rate is recognized to be suboptimal in those who have serious comorbid conditions like chronic kidney disease. In a survey of patients in the United States with chronic kidney disease, BP control was found to be a dismal 13.2%.² On a global level, hypertension is an even greater problem, with 13.5% of all deaths attributed to BP-related diseases. A majority of those who carry this disease burden belong to lower economic strata.³

It is clearly recognized that increased BP is associated with a greater risk of heart attack, stroke, and kidney disease. In fact, for persons aged 40 to 70 years, each increment of 20 mmHg in SBP or 10 mmHg in DBP actually doubles the risk of cardiovascular disease across the entire range of BP, from 115/75 to 185/115 mmHg.⁴

TABLE 1: CLASSIFICATION OF BLOOD PRESSURE (BP)

Classification	Systolic BP (mmHg)	Diastolic BP (mmHg)
Normal	<120	And <80
Prehypertension	120-139	Or 80-89
Stage 1 hypertension	140-159	Or 90-99
Stage 2 hypertension	>160	Or >100

BP, blood pressure data from <http://www.nhlbi.nih.gov/guidelines/hypertension/index.htm> (accessed April 12, 2012).

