	propranolol	Inderal, Inderal LA	
	sotalol	Betapace	
	timolol	Blocadren	
Alpha-1 blockers	doxazosin	Cardura	A drop in blood pressure upon standing up, fainting, weakness, heart palpitations, headache, nasal congestion, dry mouth.
	prazosin	Minipress	
	terazosin	Hytrin	
Alpha and beta blockers	carvedilol	Coreg	Wheezing, depression, insomnia, diarrhea, lightheadedness, dizziness, unusual tiredness or weakness, drying of the eyes, erectile dysfunction, headache, dry mouth, nasal congestion, decreased HDL cholesterol levels, lower exercise tolerance, a drop in blood pressure upon standing up, fainting, heart palpitations. Can worsen peripheral vascular disease and heart failure. Abrupt withdrawal may trigger angina or a heart attack in patients with heart disease.
	labetalol	Normodyne, Trandate	
Peripheral nerve-acting agents	guanethidine	Ismelin	A drop in blood pressure upon standing up, depression, nasal stuffiness, nightmares. Guanethidine may slow heart rate and reserpine may cause indigestion.
	reserpine	Serpalan	

Direct-acting vasodilators		
Generic name	Brand name	Side effects
hydralazine	Apresoline	Headaches, palpitations, weakness, flushing, nausea. Minoxidil may cause hair growth, fluid retention, and increased blood sugar.
minoxidil	Loniten	
Calcium-channel blockers		
Generic name	Brand name	Side effects
amlodipine	Norvasc	Headache, dizziness, edema, and heartburn. Nifedipine can cause palpitations. Diltiazem and verapamil can cause constipation and a slowed heartbeat.
diltiazem	Cardizem, Dilacor, others	
felodipine	Plendil	
isradipine	DynaCirc	
nicardipine	Cardene, Cardene SR	
nifedipine	Adalat CC, Procardia XL	
verapamil	Calan, Isoptin, others	
ACE inhibitors		
Generic name	Brand name	Side effects
benazepril	Lotensin	Cough, rash, fluid retention, high potassium levels, and loss of taste. May cause low blood pressure and fainting. Can worsen kidney impairment if narrowed arteries feed both kidneys. May cause fetal abnormalities.
captopril	Capoten	
enalapril	Vasotec	
fosinopril	Monopril	
lisinopril	Prinivil, Zestril	
quinapril	Accupril	
ramipril	Altace	

Angiotensin-receptor blockers (ARB)		
Generic name	Brand name	Side effects
candesartan	Atacand	Muscle cramps, dizziness.
eprosartan	Teveten	
irbesartan	Avapro	
losartan	Cozaar	
olmesartan	Benicar	
telmisartan	Micardis	
valsartan	Diovan	
Combination antihypertensive drugs		
Class	Generic name	Brand name
Potassium-sparing and thiazide diuretics	amiloride + HCTZ*	Moduretic

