10.0 CONCOMITANT MEDICATIONS

To be eligible for enrollment, study participants must require a minimum of three (3) anti-hypertensive medications at the time of entry into the study. Additionally, all subjects will remain on at least three (3) anti-hypertensive medications for the duration of the study.

In addition to the required regimen of hypertensive medications, all study subjects will be required to adhere to a regimen of dual antiplatelet therapy consisting of aspirin (81-325 mg daily) and clopidogrel (75 mg daily), or equivalent medications. If alternative equivalent medications are used, these should be initiated at least three (3) days prior to the implant procedure and continued for at least three (3) months post-procedure. Use of aspirin is required for the duration of study.

Appropriate management of subject's individual risk factors such as statins, smoking cessation, nutrition, diabetes will remain as standard of care and any changes to this regimen will be documented by the study team.

Subjects should be advised of the importance of continuing their medical therapy regimen without consulting with the study center. Subjects should not reduce or stop their anti-hypertensive medication dosage until the 6-month time point, at which time the Principle Investigator may decide to reduce medication as per the site's protocol.

All medications will be recorded on the Concomitant Medication log.

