11.1.2 Unanticipated Adverse Device Effects (UADE) (where applicable)

An unanticipated adverse device effect (UADE) is any serious adverse effect on health or safety or any life-threatening problem or death caused by or associated with a device, if that effect, problem, or death was not previously identified in nature, severity or degree of incidence. Anticipated adverse events are identified in Section 11.3.

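### The two relatedness levels in Section 11.2.3 have no consistent place for an adverse event that both the device and another cause could explain

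*Combined protocol and SAP*

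**What the plan says.** Section 11.2.3 has the investigator assign every adverse event to one of two levels.

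*Related* has three bullets:
- timing: "There is a clinically plausible time sequence between onset of the AE and study treatment administration; and/or"
- mechanism: "There is a biologically plausible mechanism for study treatment causing or contributing to the AE; and"
- no alternative: "The AE cannot be reasonably attributed to concurrent/underlying illness, other drugs, or procedures"

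*Not related* opens with "Evidence indicates no plausible direct relationship to the study device, such that" and then gives three grounds: inconsistent timing, an implausible mechanism, or an event that can be put down to illness, other drugs or procedures. The first two are joined by an and/or; nothing states how the third connects to them. There is no intermediate level.

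The background is the same for everyone. Section 6.0 admits only people with stage 2 resistant hypertension. Section 10.0 says that "all subjects will remain on at least three (3) anti-hypertensive medications for the duration of the study", and requires dual antiplatelet therapy around the implant with aspirin throughout.

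Relatedness is used in three places. Section 11.2 records it for every event. Section 13.0 lists it where appropriate. Section 11.1.2 defines an unanticipated adverse device effect (UADE) partly as one "caused by or associated with a device". The primary outcome in the synopsis counts all serious adverse events (SAEs) whatever their cause, together with UADEs, through six months.

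**The concern.** In this population an adverse event will often have more than one candidate explanation, and the protocol's own text supplies the competing ones. For ACE inhibitors, Section 8.1 states "May cause low blood pressure and fainting". Section 2.0 notes that "increased BP is associated with a greater risk of heart attack, stroke, and kidney disease". The device, for its part, is designed to lower blood pressure, and Section 8.10 anticipates abrupt falls after implant. Hypotension to which device and drugs both contribute is therefore a foreseeable event, and it is one that the two definitions do not classify cleanly.

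The study is small, uncontrolled and first-in-man. With no comparator, case-by-case causality is one of the main ways to separate device harm from background. A rule that removes the device label whenever something else might explain the event would make the listed device-related profile look better than it is.

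**Working it through.** The plan states no figure on this point, so the check is a logical one. Each event is described by three yes/no facts: T, plausible timing; M, plausible mechanism; A, a reasonable alternative cause.

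**Readings of *Related*.** The bullets run T and/or M, and not-A.
- Natural grouping: (T or M) and not-A.
- Minority grouping: T or (M and not-A).

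**Readings of *Not related*.**
- Any bullet suffices: not-T, or not-M, or A.
- Heading binds: not-T or not-M, so an alternative cause is not enough alone.

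| T | M | A | Related, natural | Related, minority | Not related, any bullet | Not related, heading binds |
|---|---|---|---|---|---|---|
| yes | yes | no | yes | yes | no | no |
| yes | yes | yes | no | yes | yes | no |
| yes | no | yes | no | yes | yes | yes |
| no | yes | yes | no | no | yes | yes |
| no | no | yes | no | no | yes | yes |

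The second row is the mixed-cause event.
- Natural grouping, any bullet: *Not related*.
- Natural grouping, heading binds: neither level.
- Minority grouping, any bullet: both levels.
- Minority grouping, heading binds: *Related* only.

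So one of the four combinations gives a consistent *Related*, and it needs the less natural grouping. Under the natural grouping all four rows with an alternative cause fail *Related*. The section also pulls against itself: the mechanism bullet accepts a device that merely contributed, and the next bullet withdraws that whenever another cause is reasonable. Nor are the levels exclusive elsewhere. With plausible timing, an implausible mechanism and no alternative cause, both definitions are met.

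**Scope.** Section 11.3 lists 19 anticipated items. Seven have an alternative in the protocol's text or required drugs: stroke/TIA, acute and chronic blood pressure change, recurrent hypertension, myocardial infarction, renal insufficiency and bleeding. This counts kinds of event open to the problem; it is not a misclassification rate.

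**Illustration with assumed counts.** The plan specifies no intervals; exact 95% limits are used here only to show scale at N = 20.
- Three mixed-cause events in different subjects, labelled *Related*: 3/20 = 15%, interval 3.2% to 37.9%.
- None labelled *Related*: 0/20, upper limit 1 − 0.025^(1/20) = 16.8%.
- With one such event the comparison is 1/20 = 5% (0.1% to 24.9%) against 0/20.

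**The case against.** Three stronger readings are tempting, and the documents do not support them.

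**That every hypotensive episode, stroke or bleed must be scored *Not related*.** The test is whether the event can *reasonably* be attributed elsewhere, which is a judgement on each case. Subjects enter with systolic pressure of at least 160 mmHg despite at least a month of maximally tolerated therapy and no anticipated changes. An investigator need not blame that unchanged regimen for a fall on the day after implant. The side effect quoted from Section 8.1 belongs to one drug class, which is not mandatory. Section 2.0 describes a population risk, not the cause of a particular stroke. This objection stands: the background makes an alternative easy to find but does not compel it.

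**That the UADE part of the primary outcome is seriously compromised.** Section 11.1.2 defines a UADE in its own words and does not refer to 11.2.3. Hypotension, stroke and bleeding are already anticipated in Section 11.3, so each would need unusual severity or incidence to qualify. A UADE would ordinarily also be an SAE and so be counted regardless of cause. This too stands, and leaves only a smaller effect.

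**That the rule always errs towards a safer-looking device.** The lead-in to *Related* can be met by timing, and the minority grouping yields *Related*. A bias in that direction is likely, not uniform.

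There are also safeguards. The DSMB adjudicates all SAEs and UADEs (Section 11.5) and evaluates SAEs for relationship to device or procedure (Section 16.1). Section 13.0 gives a full profile and narrative for each subject and plans no hypothesis test. But no separate causality criteria are given for the DSMB, and Section 16.1 adds only sponsor trend review for non-serious events.

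**Conclusion.** The concern holds in a limited form. Section 11.2.3 does not place mixed-cause events in exactly one level, and its natural reading favours *Not related* or no level at all. The likely result is under-labelling of device-related events by investigators, mainly non-serious ones, and possibly different codes for the same event at different sites. The effect on UADE recognition is smaller, and the all-cause SAE count does not change.

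This rests on two assumptions: that sites group the bullets in the natural way, and that the investigator finds an alternative cause reasonable in the case at hand. How often both will hold cannot be estimated from the documents; the 0/20 against 3/20 comparison is illustrative only. The wording should be corrected, but the defect does not undermine the primary analysis.

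**What to change.** Rewrite Section 11.2.3 so that each event falls in exactly one level. Replace the *Related* bullets and lead-in with a single definition: *a reasonable possibility, based on timing together with a plausible mechanism or the absence of a more likely cause, that the device or its implantation caused or contributed to the event, even if illness or concomitant drugs may also have contributed*. Limit *Not related* to events with no plausible device contribution, and state that any other event is *Related*.

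Deleting the third *Related* bullet alone would not do. Timing and/or mechanism would remain, so timing by itself could satisfy the rule over 36 months of follow-up.

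Alternatively, add a *Possibly related* level for events with a plausible device role and another possible cause, and count it as device-related in UADE screening and the Section 13.0 listings. Under either option, state that the DSMB applies the same definition under Section 16.1.

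The cost is a change to the protocol wording and the adverse event form. Somewhat more events will be labelled device-related.
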